Protocol:

Impact of Pillboxes on Medication Adherence

IRB-18-0451

NCT03861845

Primary Investigator:

[name], OTR/L, Assistant Professor

Occupational Therapy Department

Florida International University

[contact]

Email: [contact]

Version:

3

Date:

February 2019

SUMMARY OF THE RESEARCH.....	3
BACKGROUND.....	4
Scientific Background & Literature Review.....	4
RESEARCH OBJECTIVES.....	5
SUBJECT POPULATION.....	6
Duration of participation.....	6
Number of Participants.....	6
Inclusion & Exclusion Criteria.....	6
SUBJECT RECRUITMENT.....	7
Identification of Subjects & Recruitment.....	7
Incentives.....	7
METHODS & ACTIVITIES.....	8
Instrumentation & Data Collection.....	8
Intervention.....	9
Interactions.....	10
Data Analysis.....	11
BENEFITS & RISKS.....	12
Benefits to Subjects.....	12
Benefits to Society and/or Others.....	12
Reasonably Expected Risks, Harms, and/or Discomforts.....	12
Minimizing Risks, Harms, and/or Discomforts.....	12
INFORMED CONSENT.....	13
CONFIDENTIALITY & PRIVACY.....	14
Provisions to Protect Privacy.....	14
Confidentiality of Data.....	14
Breaking Confidentiality.....	14

SUMMARY OF THE RESEARCH

This study uses an experimental design to test the impact of different types of pillboxes on medication adherence. Participants in this study will be randomized to receive one of the three pillbox interventions: 1) A standard seven day a week, one-dose per day pillbox with training 2) an off-the-shelf pillbox that was purchased specifically for the individual's needs with training and education, or 3) a customized 3D printed pillbox that was designed and manufactured specifically to the individual's needs with training and education. Participants will have three visits with the research team to collect baseline data, receive the pillbox, and collect follow up data.

Risks to the study include loss of time, boredom, invasion of privacy, and medication errors. We have taken precautions to mitigate these risks. This study will improve understanding of medication adherence and potentially help us better address poor medication adherence which needlessly causes morbidity, mortality, and costs over \$300 million in unnecessary healthcare costs each year.

BACKGROUND

Scientific Background & Literature Review

Many individuals do not take medicine as prescribed resulting in declines in health and function. Pillboxes are a cost effective and easy to implement intervention that can help people better take their medications as prescribed. While some studies find that pillboxes can increase medication adherence as much as 5% other studies find that pillboxes have no effect. We hypothesize that to be effective pillboxes must be customized to the client's needs and be part of a package of services involving training on the device and education. The purpose of this study is to understand the impact of customized pillboxes on medication adherence.

1. Vlasnik, J. J., Aliotta, S. L., & DeLor, B. (2005). Medication adherence: factors influencing compliance with prescribed medication plans. *The Case Manager*, 16(2), 47-51.
2. Bartlett, R. J. (2018, September). Characteristics of Adults Managing Vitamins/Supplements and Prescribed Medications- Who Is Using, Not Using, and Abandoning Use of Pillboxes?: A Descriptive Study. *PubMed*, 32(5), 231-239. doi: 10.1097/NUR.0000000000000395
3. Defanti e Souza, F. and da Silva Santana, C. (2013) A descriptive study about the use of pillboxes by older adults. *Health*, 5, 103-109. doi: 10.4236/health.2013.512A014
4. Bartlett, R. J., Knisely, M. R., Boyer, K., & Pike, C. (2017). Pillbox intervention fidelity in medication adherence research: A systematic review. *Nursing Outlook*, 65(4), 464-476. doi:10.1016/j.outlook.2016.12.011

RESEARCH OBJECTIVES

The purpose of this study is to:

- Understand the impact of pillbox customization on medication adherence
- Understand the impact of pillbox customization on device satisfaction
- Test the feasibility of the research methodology

SUBJECT POPULATION

Duration of participation

Interaction 1: Screening: .5 hrs

Interaction 2: Informed Consent & Evaluation: 2 hrs

Interaction 3: Dispersion of pillboxes: 1 hr

Interaction 4: Follow-up Data Collection: 1.5 hrs

Total time commitment- approximately 5 hrs

Number of Participants

We seek to enroll as many as 40 participants in the study. This means we may screen as many as 120 individuals to identify the 40 study participants.

Inclusion & Exclusion Criteria

To be included in this study participants must be 18 years of age or older, speak English, and be prescribed to take two or more medications per day, and manage their own medications.

Participants will be excluded if they have a significant cognitive impairment, unwilling to use a novel pillbox, or are unable to meet with the research team.

SUBJECT RECRUITMENT

Identification of Subjects & Recruitment

We will recruit through word of mouth, by sharing study information with local organizations that serve adults who take medications, and snowballing (asking participants to share the recruitment flyer with other individuals who take medications). We will also post electronic flyers on social media.

Incentives

Participants who complete all study procedures will earn up to \$20 in gift cards and a pillbox. On the 1st and 3rd visit, participants will receive a \$10 gift card. On the 2nd visit, the participant will receive a pillbox worth no more than \$15.

METHODS & ACTIVITIES

Instrumentation & Data Collection

Below is a description of each data collection tool.

- Screener Survey - ensures that the individual meets the eligibility criteria for the research study. This also allows the individual to describe their preferred contact method.
- Adherence to Refills and Medication Scale - 12 question Likert-like survey investigating medication adherence
- Demographics Questionnaire (Characteristics of Respondents [CORE] Survey) - Describes the participants background including race, ethnicity, gender, diagnoses, family situation, etc.
- Performance Assessment of Self Care Skills Medication Subtest - This performance-based assessment asks participants to sort a placebo medication. Participants are scored on their independence, safety, and adequacy in performing the task.
- Canadian Occupational Performance Measure - Participants discuss their daily routine. They score their performance of everyday activities on their importance, satisfaction, and performance.
- Quebec User Evaluation of Satisfaction with Assistive Technology - 12 item Likert-scale questionnaire evaluates how satisfied participants are with their assistive device and their related services that they experience.
- Medication Management Instrument For Deficiencies in the Elderly - Examines how much the participant knows about their medications, if they know how to take their medications, and if they know how to procure their medications. Also provides their complete medication list.
- Exit Interview - Participants will be interviewed regarding their experiences within the study.
- Audio recordings - All interactions will be audio recorded. The PI will assess the researcher assistant's fidelity to the protocol.

Intervention

Participants in this study will randomized to receive one of the three pillbox interventions:

1. Standard Pillbox - Participants will receive a standard seven day a week, one-dose per day pillbox. The participant will receive basic training on using the pillbox.

Figure 1. Standard Pillbox

2. Off-the-Shelf Pillbox – Participants will receive an off-the-shelf pillbox that was purchased specifically for the individual’s needs from a store like CVS, Walgreens, or Amazon. The participant will also receive with training and education on using the pillbox.

3. Customized 3D printed Pillbox – The participants will receive a customized 3D printed pillbox that was designed and manufactured specifically to their individual needs.

Interactions

Research participants will occur in 4 interactions.

1. Screening

Up to .5 hrs on participant's own time on computer or the participant may be screened verbally at a time of their choosing
Assessments: screener survey

2. Informed Consent and Evaluation

Up to 2 hrs

Lab at FIU or preferred location where both parties (participants and evaluators) agree on
Assessments: COPM, QUEST, PASS, MedMaIDE, ARMS, and Demographics Questionnaire

3. Dispersion of pillboxes

Up to 1 hr

Lab at FIU or preferred location where both parties (participants and evaluators) agree on

4. Follow-up Data Collection

Up to 1.5 hrs

Lab at FIU or preferred location where both parties (participants and evaluators) agree on.

Data Analysis

Researchers will evaluate all variables using descriptive statistics. We will also explore the relationship between variables using approaches such as Pearson's product-moment correlation. Using this information, we will evaluate the appropriateness of the data against the assumptions for commonly used statistical approaches. Data may be normalized to increase appropriateness for the test. Then we will engage in means-testing using approaches such as t-tests, ANOVAs, Mann-Whitney U, Kruskal-Wallis analysis of variance, etc. as determined by looking at the appropriateness of the variable for that procedure. Specifically, we aim to compare means within and between groups on scores from the COPM & QUEST.

For qualitative data, we will use a grounded theory approach, consisting of open, axial, and selective coding to generate themes describing the participants answers to open ended questions.

BENEFITS & RISKS

Benefits to Subjects

There are no direct benefits to participants.

Benefits to Society and/or Others

Information learned from this study will be used to progress research and improve medication adherence for adults.

Reasonably Expected Risks, Harms, and/or Discomforts

Risk 1) Loss of time, low likelihood, low severity

Risk 2) Boredom, low likelihood, low severity

Risk 3) Invasion of privacy, low likelihood, low severity

Risk 4) Leakage of information, low likelihood, moderate severity Risk 5) Medication errors, low likelihood, moderate severity

Minimizing Risks, Harms, and/or Discomforts

Risk 1) Loss of time: Participants can select when and how they participate to limit loss of time related to travel. Research team will work with participants in an expedient manner.

Risk 2) Boredom: Participants will be informed that they can stop the survey or interview at any time. Participants will be informed that they can take breaks as needed during the survey or interview.

Risk 3) Invasion of privacy: Participants will be educated that they do not have to talk about topics or answer survey items that feel invasive.

Risk 4) Leakage of information: Electronic data will be stored on secure devices and servers. Identifying information (e.g., informed consent) will be stored separately from survey and interview data.

Risk 5) Medication errors: Participants will be required to verbalize how to use the pillboxes. They will also be required to correctly demonstrate how to use the pillboxes with placebo medication (i.e. tic-tacs or similar candy). Participants who cannot verbalize and demonstrate correctly use of the pillbox will be removed from study participation.

INFORMED CONSENT

Informed consent will be provided in a quiet and private environment. Participants will be given as much time as they need to consider participation and ask questions of the research team. Signed informed consent forms will be stored in the PI's office.

CONFIDENTIALITY & PRIVACY

Provisions to Protect Privacy

- Data will be de-identified
- Identified information (i.e. informed consents and the master key) will be stored separately from the study data.
- Physical data will be stored securely in a locked filing cabinet in the PIs locked office.
- Electronic data will be stored on the secure FIU OneDrive and backed up on an encrypted and password protected external hard drive which is stored in a locked filing cabinet in the PIs office.
- Only members of the research team will have access to the data

Confidentiality of Data

- Informed consents will be stored in a locked filing cabinet in the PIs locked office.
- Study data will be collected with the assistance of Qualtrics and will be stored in FIU Qualtrics during data collection. After data collection, the data will be removed from Qualtrics and stored on FIU One drive. The study data will only be associated with the participants ID Code.
- Audio recordings will be stored on FIU One Drive.
- The Master Key will be stored on FIU One Drive separate from all study data.
- The study data and audio/video recordings will be backed up on to an encrypted and password protected external hard drive which will be stored in a locked filing cabinet in the PIs office.
- Only members of the research team will have access to the data.

Breaking Confidentiality

If participant's interview suggests abuse or neglect to themselves or others, it is necessary to break confidentiality. In the unlikely event that a participant reports is at serious risk to harm themselves or others, the participant will be reported to the appropriate authorities.

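### Entry ignores adherence and no analysis uses baseline ARMS, so an adherence benefit of customisation may be diluted by participants with no room to improve

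*Combined protocol and SAP*

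**What the plan says.** The Summary of the Research says the study may "potentially help us better address poor medication adherence", and the first entry under Research Objectives is "Understand the impact of pillbox customization on medication adherence".

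Under Inclusion & Exclusion Criteria, entry requires adulthood, English, and that people "be prescribed to take two or more medications per day, and manage their own medications". The exclusions read: "Participants will be excluded if they have a significant cognitive impairment, unwilling to use a novel pillbox, or are unable to meet with the research". Good adherence is not among them. The screener survey, described under Instrumentation & Data Collection, "ensures that the individual meets the eligibility criteria for the research study"; no adherence item is described for it. Recruitment is aimed at adults who take medicines in general.

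The adherence instrument, ARMS, is a "12 question Likert-like survey investigating medication adherence". It first appears at the consent and evaluation visit (Interactions, item 2): "Assessments: COPM, QUEST, PASS, MedMaIDE, ARMS, and Demographics Questionnaire". No cut-off is attached to it.

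The Data Analysis section describes all variables, explores relationships between them and then compares means, singling out COPM and QUEST. It mentions no stratification, subgroup or adjustment by baseline adherence. Number of Participants gives a maximum of 40 and adds: "This means we may screen as many as 120 individuals to identify the 40 study participants".

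**The concern.** The trial is motivated by poor adherence, but nothing at entry or in the analysis separates people who have an adherence problem from people who do not. A participant already at the best ARMS score cannot gain on ARMS from any of the three boxes. If such people stay where they are, they pull every between-arm difference towards zero.

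With at most 40 people over three arms there is little margin for this. A null adherence result would be hard to read: customisation might not help, or too few of those enrolled might have had anything to gain.

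**Working it through.** **No figure to reproduce.** The protocol gives no sample-size calculation behind the 40, so the figures below are an illustration.

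**Inputs.**
- From the protocol: at most 40 participants, three arms, up to 120 screened.
- Assumed: 1:1:1 allocation (40/3 = 13.3, taken as 13 per arm), one pairwise two-sided t-test at 0.05, and SD = 1 for the ARMS outcome.
- Assumed: a share f at ceiling, equal across arms, with no change in any arm. The documents give no value for f; 20%, 40% and 50% are scenarios.

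**Starting effect.** The t-test power comes from the noncentral t distribution with 2n − 2 degrees of freedom and noncentrality d√(n/2). At n = 13, power is 80% when d = 1.145. This value is solved to give 80% and is not a forecast.

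**Dilution.** The mean contrast over all participants is (1 − f) × 1.145. Two variance cases bracket the loss:
- *A, SD unchanged.* Ceiling participants vary as much as everyone else, so the standardised effect is (1 − f)d.
- *B, no variance of their own.* Ceiling participants change by exactly 0. The variance is (1 − f) in the comparison arm and (1 − f) + f(1 − f)d² in the better arm. The standardised effect is (1 − f)d divided by the square root of the average of the two. For f = 0.2 this is 0.916/√((1.010 + 0.800)/2) = 0.963.

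**Restricted analysis.** Only those with room to improve are compared: 13(1 − f) per arm at the full d = 1.145.

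Case B and the restricted analysis were also simulated, letting the number at ceiling in each arm vary by chance.

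| f | A: effect, power | B: effect, power (formula / simulated) | Restricted: n per arm, power (formula / simulated) |
|---|---|---|---|
| 0 | 1.145, 80% | 1.145, 80% | 13, 80% |
| 0.2 | 0.916, 61% | 0.963, 65% / 66% | 10.4, 70% / 69% |
| 0.4 | 0.687, 39% | 0.790, 49% / 49% | 7.8, 56% / 54% |
| 0.5 | 0.573, 29% | 0.703, 40% / 40% | 6.5, 47% / 45% |

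**Gain from restricting.**
- Case A, by formula: 70 − 61 = 9, 56 − 39 = 17 and 47 − 29 = 18 points.
- Case B, simulated: 69 − 66 = 3, 54 − 49 = 5 and 45 − 40 = 5 points.

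**Screening load of an entry cut-off.** If the present yield of one enrolled per three screened already reflects the existing criteria, filling 40 places needs 120/(1 − f) screened: 150, 200 and 240 at f = 0.2, 0.4 and 0.5.

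**The case against.** The case for leaving the plan alone has several parts.

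- **The ceiling share is unknown.** A reader might infer that a large part of the sample will be at the best score. The criteria permit such people, but no ARMS distribution is given, and the best answer on all 12 items is a strict condition. This stands, so the percentages are scenarios.
- **Adherent people could worsen.** A reader might infer that in a fully adherent person no box can do better than another. The protocol itself lists medication errors as a risk, everyone receives a device, and the arms could disrupt a good routine to different degrees. This stands, and it is why the all-participant result must be kept.
- **The loss depends on the variance assumption.** Under case B the restricted analysis gains only 3 to 5 points. This stands, though the gain does not vanish or reverse in any scenario run.
- **ARMS is not wholly absent from the analysis.** It falls within the variables to be described and explored. This stands. What is missing is any named adherence contrast and any use of the baseline score in one.
- **Broad entry suits a feasibility study, and the trial is small anyway.** Feasibility and satisfaction are objectives, and satisfaction need not share this ceiling. Power is only 23% at 0.5 SD and 50% at 0.8 SD with no dilution at all. So broad entry is defensible, and no handling of baseline adherence makes 40 people adequate for moderate effects. Adherence is nevertheless the first objective, and the remedy costs little.
- **Near-ceiling participants remain.** Excluding only those at the exact best score is a partial cure. This stands.

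**Conclusion.** The concern holds in a limited form. The plan admits people with no room to improve on ARMS and nowhere takes account of baseline ARMS, so a real adherence benefit may be diluted. In the scenarios, an effect with 80% power undiluted would have about 61–66%, 39–49% or 29–40% with 20%, 40% or 50% at ceiling. Restricting to those who can improve recovers between 3 and 18 percentage points, depending mainly on the variance assumption.

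These figures rest on equal allocation, a single pairwise test at 0.05, a back-solved effect of 1.145 SD, and ceiling participants who stay unchanged in every arm.

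The documents do not support reading the broad eligibility as an error. Nor do they support the view that tighter entry could be had within the planned screening. The 120 was stated for the present criteria and is not shown to hold spare capacity.

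**What to change.** Leave eligibility as it is and add to Data Analysis, before outcome data by arm are examined:

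1. The main answer to objective 1 is the between-arm ARMS contrast among participants whose baseline ARMS is worse than the best possible score. State which arms are compared, and state that ARMS is repeated at the follow-up visit, whose entry under Interactions lists no instruments.
2. The all-participant ARMS contrast, adjusted for baseline ARMS, is reported beside it, so that worsening among adherent people is visible.
3. The number at the best baseline score is reported by arm.
4. Satisfaction analyses keep everyone.

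The subgroup is defined by a score taken before the boxes are handed out, so the randomised comparison is kept. The protocol does not say when allocation is made; the baseline ARMS should be completed before the participant knows it. The contrast should be between arms, because within-arm change in a group selected for imperfect scores is open to regression to the mean.

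The cost is wording, plus a smaller and narrower group for one contrast. If nobody is at ceiling, nobody is dropped.

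An ARMS cut-off at screening is an optional design choice only. It could raise screening from 120 to about 150–240 at 20–50% ceiling if the 3:1 yield holds, and it would place ARMS ahead of the consent visit.

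### The test and any transformation are chosen variable by variable after the data have been examined, so the plan does not fix whether it will report the mean difference it aims for

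*Combined protocol and SAP*

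**What the plan says.** The Data Analysis section (under METHODS & ACTIVITIES) sets out a sequence.

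- First, "Researchers will evaluate all variables using descriptive statistics", and correlations between variables are explored.
- With that information in hand, "we will evaluate the appropriateness of the data against the assumptions for commonly used statistical approaches".
- A transformation is optional: "Data may be normalized to increase appropriateness for the test". Neither the method nor the trigger is given.
- Then comes "means-testing using approaches such as t-tests, ANOVAs, Mann-Whitney U, Kruskal-Wallis analysis of variance, etc", with the choice made "as determined by looking at the appropriateness of the variable for that procedure".
- The target is stated last: "Specifically, we aim to compare means within and between groups on scores from the COPM & QUEST".

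No default test, decision threshold, significance level or sidedness appears anywhere in the document. It also does not say whether data are seen by arm or pooled when the test is chosen.

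**The concern.** This is more than a missing detail. The plan states a positive rule, and under that rule the data decide what is estimated. Mean-based tests, rank tests and tests on a transformed scale answer different questions, and only an analysis on the raw mean scale answers the one the plan poses. Two scores in the same trial could go down different routes, and their results could not then be set side by side.

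The correlation step does not help. Correlations between variables do not diagnose normality or equal variance within arms.

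A second question is whether choosing the test from the data distorts the error rate. That has to be sized, because the answer depends on how the choice is made.

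**Working it through.** **Inputs.** From the documents: three arms ("randomized to receive one of the three pillbox interventions") and an upper limit on size ("We seek to enroll as many as 40 participants in the study"). Assumed, because the documents give no figure: near-equal arms (14/13/13), two-sided alpha 0.05, and all score distributions. The plan states no error rate, power or sample-size derivation, so there is no figure of its own to reproduce.

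**Step 1: do the listed routes target the same quantity?**

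- t-test or ANOVA on raw scores: difference in mean points. This matches the aim.
- Mann-Whitney U or Kruskal-Wallis: whether scores in one arm tend to exceed those in another. This matches a comparison of means only under extra conditions, such as a pure shift in location.
- Log or normal-score transformation: a difference on a new scale, not in COPM or QUEST points. If normalising means only a linear rescaling, the test result is unchanged and so is any departure from normality.

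An example with equal means: X is exponential with mean 1, and Y is normal with mean 1 and SD 0.4. Ignoring the negligible chance that Y is negative, P(X < Y) = 1 − E[exp(−Y)] = 1 − exp(−1 + 0.4²/2) = 1 − exp(−0.92) = 0.60. The means are equal, but the Mann-Whitney target is 0.60 rather than 0.50.

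**Step 2: how stable is the route?** Suppose a Shapiro-Wilk check at 5% on the residuals decides. For an assumed 12-item score with a ceiling, it rejects normality in 43% of trials. The same underlying distribution thus goes to ranks in 43% of trials and to means in 57%. For an assumed rounded 1-10 score the split is 21% and 79%. In a single arm of 13, the check rejects for about 14% of samples with either of these shapes.

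**Step 3: type I error when all arms share one distribution** (10,000 trials per row; simulation SE = √(0.05 × 0.95 / 10,000) = 0.2 points; figures in %).

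| Assumed shape | ANOVA | Kruskal-Wallis | Check picks one of these | Check with log step | Smallest of three p-values |
|---|---|---|---|---|---|
| Normal | 4.8 | 4.5 | 4.9 | 4.9 | 6.0 |
| Lognormal | 3.7 | 4.7 | 4.9 | 5.4 | 6.9 |
| Exponential | 4.5 | 4.9 | 5.4 | 6.2 | 7.7 |
| 12-item, ceiling | 5.3 | 4.8 | 5.7 | 5.7 | 6.6 |
| Rounded 1-10 | 4.7 | 4.4 | 4.7 | 4.8 | 6.0 |

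The last column takes the smallest p-value among ANOVA, log ANOVA and Kruskal-Wallis. Separate runs at 13/13/14 agree: 5.0 to 5.5% when a check picks the test, 5.9 to 7.2% for the smallest of three p-values, and 6.1 to 7.6% for the smallest of four.

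**Step 4: equal means but different shapes, 13 v 13** (rejection at 0.05, %).

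| Assumed pair | Welch t | Mann-Whitney | Check picks one |
|---|---|---|---|
| Exponential v normal | 7.5 | 14.3 | 14.4 |
| Lognormal v normal | 10.2 | 19.8 | 19.5 |
| Mirror-image skew (two runs) | 7.1 to 7.7 | 13.2 to 13.7 | not run |

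In these pairs the rank test rejects equal means about twice as often as the Welch test. The gap depends on shape: in a three-arm example with one two-humped arm, Kruskal-Wallis gave 8.9% and ANOVA 6.9%.

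**The case against.** The strongest defence is that the plan chooses tests by their assumptions, not by their results. Checking assumptions is ordinary practice, and a mechanical check keeps the error rate close to 5%. The study has at most 40 participants, feasibility is one of its three objectives, and the wording is exploratory. Descriptive statistics are planned for every variable, so raw arm means can be reported beside a rank test.

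Much of this stands. Three stronger readings are tempting, and the documents do not support them.

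- A reader might infer that a nominal 5% level is broken. No level is stated. The 6 to 8% figures mostly require picking the analysis by its p-value, which the plan does not describe.
- A reader might infer that analysts who know the arms choose the test. The documents do not say how the data are viewed at that point. A choice blind to arm would lessen the concern.
- A reader might infer that no mean difference would be available to a later trial. The planned descriptive statistics could supply one, though the plan does not commit to a difference with a confidence interval.

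The defence does not remove the central point. No rule for the assumption check is given, so the mechanical version is a charitable reading. The other two objectives concern the effect of customization on adherence and on device satisfaction, and between-group testing is planned. The mismatch between an aim about means and a list containing rank tests does not depend on any simulation.

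**Conclusion.** The point holds for the estimand and only weakly for the error rate. The plan leaves open, score by score, whether the result will be a mean difference, a rank comparison or a transformed-scale difference, and two of its four named tests can conflict with its stated aim.

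Error control cannot be verified because no alpha and no decision rule are given. At an assumed two-sided 0.05 with common shapes across arms, it stays near 5% when a check picks between ANOVA and Kruskal-Wallis. It reaches 6.2% for one shape when a log step is added, and about 6 to 8% when results drive the choice. The 13 to 20% figures for Mann-Whitney apply only to the hypothesis of equal means when arms differ in shape. All of these rest on assumed distributions, arm sizes and alpha.

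**What to change.** Replace the selection rule with one analysis fixed in advance for each COPM, QUEST and ARMS score.

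- **Between arms:** the difference in mean raw follow-up score with a 95% CI, adjusted by ANCOVA for the baseline score collected at the Informed Consent and Evaluation interaction. Use robust standard errors or a studentised permutation p-value, because arms are small and shapes may differ. A plain permutation test of the mean difference is not enough: with mirror-image skew it rejected equal means in 7.5 to 7.9% of runs. With normal SDs of 2 v 1 and arms of 10 v 13 it rejected in 6.8%, against 4.8% for Welch.
- **Within arms:** the mean raw change with a 95% CI.
- **Also state** alpha and sidedness. Keep rank-based and transformed analyses as labelled sensitivity analyses, and stop using correlations between variables as an assumption check.

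The follow-up interaction lists no instruments, so the text should confirm that these three scores are repeated there. It should also say which device the baseline QUEST rates.

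The cost is a few sentences and a little code, with no extra participants or visits. The downside is a slight loss of power against whichever test happens to suit a given data shape best. The recommended ANCOVA was not itself simulated. The Welch results (7.1 to 10.2% with unequal shapes) show that mean-based tests at this size can also exceed 5%, so the interval should carry more weight than the p-value.

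### Adherence is the study's purpose and first objective, but the analysis names only COPM and QUEST for comparison, and nothing commits to a follow-up ARMS or its between-arm comparison

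*Combined protocol and SAP*

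**What the plan says.** **Aim.** The Summary of the Research states: "This study uses an experimental design to test the impact of different types of pillboxes on medication adherence". The Background repeats it: "The purpose of this study is to understand the impact of customized pillboxes on medication adherence". The first entry under Research Objectives is "Understand the impact of pillbox customization on medication adherence". Device satisfaction is the second objective, and the third is "Test the feasibility of the research methodology".

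**Instruments.** Instrumentation & Data Collection describes ARMS as a 12-question survey of medication adherence. QUEST is described as rating satisfaction with the assistive device and related services, and COPM as rating everyday activities. PASS is a placebo-sorting task. MedMaIDE covers what participants know about their medicines and about taking and obtaining them.

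**Schedule.** The Summary promises follow-up in general terms: "Participants will have three visits with the research team to collect baseline data, receive the pillbox, and collect follow up data". Under Interactions, Interaction 2 (before the pillbox) lists COPM, QUEST, PASS, MedMaIDE, ARMS and the demographics form. Interaction 4 (follow-up) gives a duration of up to 1.5 hours and a place, but no instrument. No time from dispensing to follow-up is stated.

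**Analysis.** Data Analysis promises descriptive statistics for all variables, exploratory correlations, and means-testing by whichever of several methods suits the variable. It then becomes specific: "Specifically, we aim to compare means within and between groups on scores from the COPM & QUEST".

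**The concern.** The one sentence that says which scores will be compared between randomized groups leaves out the outcome that the study exists to examine. Objective 2 has an instrument and a named comparison. Objective 1 has an instrument, but no named follow-up measurement and no named comparison.

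Two things are at stake. If ARMS is not repeated after the pillbox is given, no later analysis can recover post-pillbox adherence. If it is repeated, the test, any transformation and the choice among three pairwise contrasts are all left open, and could be settled after the data are seen.

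**Working it through.** The main check is textual. The protocol gives no figure to reproduce on this point.

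**Step 1: trace each objective to a measurement and a comparison.**

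| | Adherence (objective 1) | Device satisfaction (objective 2) |
|---|---|---|
| Instrument described for it | ARMS | QUEST |
| Listed before the pillbox | yes | yes |
| Listed at follow-up | no instrument listed | no instrument listed |
| Follow-up implied elsewhere | not by any specific sentence | yes, by the planned within-group comparison |
| Between-arm comparison named | no | yes |

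COPM is also named for comparison but is not described as an adherence measure. So 0 of the 2 named scores are described as measuring adherence. PASS and MedMaIDE are neither described as adherence measures nor named for comparison.

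**Step 2: ask whether the general sentences fill the gap.** Descriptive statistics on all variables would be satisfied by baseline ARMS alone. Means-testing depends on a judgement of each variable's suitability and names no variable. The promise of follow-up data names no instrument. Each sentence allows an adherence comparison, and none requires it.

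**Step 3: what an open contrast could cost.** Inputs: at most 40 participants and three arms (protocol); equal allocation, normal data and no true difference (assumed). 40/3 is about 13 per arm, so the pooled error df = 3 × 13 − 3 = 36.

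- Three pairwise t tests, each two-sided at 0.05 with pooled SD and no gate: at least one is significant when the largest mean difference passes t(0.975, 36) = 2.028. On the studentized-range scale that is √2 × 2.028 = 2.868, and P(Q > 2.868; 3 groups, 36 df) = 0.120. A simulation of 200,000 trials gave 0.118. Both are about 12%.
- Pairwise tests only after a significant ANOVA at 0.05: with no true difference the gate opens 5% of the time, so the chance is capped at 5%. Simulation gave 0.050.

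**Step 4: what the contrasts would mean.** The Background hypothesis is that a pillbox must be customized and "be part of a package of services involving training on the device and education". In the Summary, the standard arm receives training, while the off-the-shelf and 3D printed arms receive training and education. On that description, 3D printed versus standard combines customization with education, and 3D printed versus off-the-shelf holds training and education the same. The Intervention section, however, gives training and education to the off-the-shelf arm and mentions neither for the 3D printed arm. What the second contrast isolates depends on which description applies.

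**The case against.** The strongest reply is that the sentence naming COPM and QUEST is not exclusive. The study is designed to test an effect on adherence, follow-up data are promised, all variables are to be described, and means-testing is open to any suitable variable. Read together, an adherence comparison is a natural expectation. This stands as an account of intent and permission. It does not supply a commitment to measure or compare.

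A reader might go further and infer that adherence was dropped from follow-up, because ARMS is listed only before the pillbox. The documents do not support that. Interaction 4 lists no instrument at all, not even COPM and QUEST, whose repeat the within-group comparison implies. The Exit Interview is likewise described but assigned to no interaction. The lists are plainly incomplete, so the missing ARMS entry is weak evidence either way.

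Nor is 12% the plan's error rate. Data Analysis also mentions ANOVA and Kruskal-Wallis, the usual tests for three groups, and commits to neither route. The range is about 5% to 12%. It would apply equally to COPM and QUEST, so it bears on leaving the contrast open and does not measure the adherence gap.

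Finally, this is a small study ("We seek to enroll as many as 40 participants in the study") with a feasibility objective. That limits how precise any adherence estimate can be. It does not remove the gap, because adherence is stated separately and first.

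**Conclusion.** The concern holds as a gap between the stated purpose and the named analysis. The protocol can be carried out to the letter and give no between-arm adherence result. It does not show that adherence will go unmeasured, or that the design cannot address it.

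This conclusion rests on the wording alone and needs no statistical assumption. The 5% to 12% range is secondary. It assumes 13 per arm, normal data and no true difference. Thirteen is towards the upper end, because 40 is a ceiling and participants who cannot demonstrate correct pillbox use are removed.

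The gap is worth closing before follow-up data are collected, since a follow-up ARMS that was not taken cannot be reconstructed.

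**What to change.** 1. Under Interaction 4, list ARMS together with COPM and QUEST, and state the time from dispensing to follow-up. The documents give none, so the study team must set it.
2. In Data Analysis, name for objective 1 the between-arm comparison of follow-up ARMS adjusted for baseline ARMS (ANCOVA), reported as estimates with 95% confidence intervals. This uses the baseline score already collected.
3. Fix the leading contrast in advance and report the other two as secondary, or require an overall three-arm test before any pairwise tests.
4. Before choosing the contrast, reconcile the Summary and Intervention descriptions of training and education in the 3D printed arm, and state whether the question is customization alone or customization combined with education.
5. Name QUEST as the measure for objective 2.

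Items 1 and 2 close the gap itself. Item 3 limits choices made after the data are seen.

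The cost is protocol wording and one repeated 12-item questionnaire at an existing visit, with no extra participants. No instrument durations are given, so its fit within the 1.5-hour visit must be checked. The team also gives up some freedom over which contrast to lead with.
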